## **Glossary of Terms**

ABBREVIATION	DEFINITION OR DESCRIPTION
6MWT	6 Minute Walk Test
ADL	Activities of Daily Living
AE	Adverse Event
AKI	Acute Kidney Injury
AT	As-Treated (Population)
BMI	Body mass index
BNP	B-type Natriuretic Peptide
CABG	Coronary Artery Bypass Grafting
CBC	Complete Blood Count
CEC	Clinical Events Committee
CMP	Comprehensive Metabolic Panel
CI	Confidence Interval
CIP	Clinical Investigation Plan
CSHA	Canadian Study of Health and Aging
CSR	Clinical study report
DSMB	Data Safety Monitoring Board
EDC	Electronic Data Capture
Echo	Echocardiogram
eGFR	Estimated Glomerular Filtration Rate
GGT	Gamma-Glutamyl Transferase
GHER	Global Health Economics and Reimbursement
HF	Heart Failure
INR	International Normalized Ratio
KCCQ	Kansas City Cardiomyopathy Questionnaire
KM	Kaplan-Meier
LDH	Lactic Acid Dehydrogenase
MAE	Major Adverse Event
MI	Myocardial Infarction
MVARC	Mitral Valve Academic Research Consortium
NT-proBNP	N-terminal pro B-type Natriuretic Peptide
NYHA	New York Heart Association
OR	Operating Room
PCI	Percutaneous Coronary Intervention
PP	Per-Protocol (Population)

		$\checkmark$
	U	
-	-	
		Ľ

Statistical Analysis Plan for TRISCEND Study (2019-06)

For Use Only by Affiliates of Edwards

Lifesciences

ABBREVIATION	DEFINITION OR DESCRIPTION
PT	Prothrombin Time
PTT	Partial Thromboplastin Time
PVL	Paravalvular Leak
QoL	Quality of Life
SAE	Serious Adverse Event
SAP	Statistical Analysis Plan
SAS	Statistical Analysis System (software)
SD	Standard Deviation
SF-12	12-Item Short Form Health Survey
SF-36	36-Item Short Form Health Survey
STS	Society of Thoracic Surgery
TEE	Transesophageal echocardiogram/echocardiography
TMF	Trial Master File
TMTT	Transcatheter Mitral and Tricuspid Therapies
TR	Tricuspid Regurgitation
TTE	Transthoracic echocardiogram/echocardiography
TTV	Transcatheter Tricuspid Valve
TV	Tricuspid Valve
UADE	Unanticipated Adverse Device Effect
VKA	Vitamin K Antagonists

E	Revision Da

Edwards

Statistical Analysis Plan for TRISCEND Study (2019-06)

## 1. INTRODUCTION

This statistical analysis plan (SAP) specifies the statistical methods to be implemented for the analysis of data collected within the scope of Edwards Lifesciences's Protocol #2019-06 (Edwards EVOQUE Tricuspid valve Replacement: Investigation of Safety and Clinical Efficacy after replacemeNt of tricuspid valve with transcatheter Device (TRISCEND Study)) (US) and provides detailed instructions as to how each analysis will be performed.

## 2. STUDY DESIGN

### 2.1 Study Objectives

The objectives of this feasibility study are to:

- Evaluate the safety and performance of the EVOQUE system
- Provide guidance for future clinical study designs utilizing the EVOQUE system
- Provide guidance for future EVOQUE system development efforts

#### 2.2 Overall Study Design and Plan

This is a prospective, single-arm, multi-center study to evaluate the safety and performance of the EVOQUE system in the treatment of patients with at least moderate TR and signs of, symptoms from, or prior heart failure hospitalizations for TR.

Up to 200 patients (upon FDA approval) will be enrolled in this study at up to 30 investigational sites (upon FDA approval). Subjects out of US will also be included in the analyses.

Enrolled study patients will be assessed at the following intervals: Screening/baseline, Procedure, Discharge, 30 days, 6 months, 1 year, 2 years, 3 years, 4 years, and 5 years post-procedure.

#### 2.3 Sample Size Consideration

This is a multi-center, prospective, single-arm study. Up to 200 patients (upon FDA approval) will be enrolled in this study at up to 30 investigational sites (upon FDA approval). This sample size was established based on typical sample sizes for feasibility studies, and no statistical justification was utilized. This sample size is considered adequate to evaluate the safety and performance of the EVOQUE System.

## 3. STUDY ENDPOINTS

#### 3.1 Safety Endpoints

Safety will be analyzed as a composite endpoint of Major Adverse Events (MAEs) at 30 days post-enrollment which includes:

Cardiovascular mortality

### Statistical Analysis Plan for TRISCEND Study (2019-06)

- Myocardial infarction (MI)
- Stroke
- Renal complications requiring unplanned dialysis or renal replacement therapy
- Severe bleeding (includes fatal, life-threatening, extensive, or major bleeding, as defined by MVARC)
- Non-elective tricuspid valve re-intervention, percutaneous or surgical
- Major access site and vascular complications
- Major cardiac structural complications
- Device-related pulmonary embolism

#### 3.2 **Performance Endpoints**

#### **Device Success**

• Device success is achieved if the study device is deployed as intended and the delivery system is successfully retrieved as intended at the time of the patient's exit from the OR/cardiac catheterization laboratory. This endpoint will have a per device analysis performed.

#### Procedural Success

• Procedural success is "device success" without clinically significant paravalvular leak (PVL) on a transthoracic echocardiogram (TTE, assessed by the echo core lab) at time of discharge. This endpoint will have a per patient analysis performed.

#### Clinical Success

• Clinical success is "procedural success" without any MAEs at 30 days. This endpoint will have a per patient analysis performed.

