5.1. Safety Endpoint

Safety will be analyzed as a composite endpoint of Major Adverse Events (MAEs) at 30 days post-enrollment which includes:

- Cardiovascular mortality
- Myocardial infarction (MI)
- Stroke
- Renal complications requiring unplanned dialysis or renal replacement therapy
- Severe bleeding (includes fatal, life-threatening, extensive, or major bleeding, as defined by MVARC)³
- Non-elective tricuspid valve re-intervention, percutaneous or surgical
- Major access site and vascular complications
- Major cardiac structural complications
- Device-related pulmonary embolism

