An adverse event can be related both to the study procedure and the study device. Complications of procedures are considered not related if the said procedures would have been applied to the patients also in the absence of investigational device use/application.

In some particular cases the event may not be able to be not adequately assessed because information is insufficient or contradictory and/or the data cannot be verified or supplemented. The sponsor and the Investigators will make the maximum effort to define and categorize the event and avoid these situations.

Clinical Frailty Scale[®]

A 9 point single question administered to measure frailty. Developed by the Canadian Study of Health and Aging (CSHA).

Death

(MVARC 2015 Definition)

A. Cardiovascular Death

Cardiovascular death is defined as any of the following contributing conditions:

- Heart failure (sub-classified into left ventricular vs. right ventricular dysfunction)
- Myocardial infarction
- Major bleeding
- Thromboembolism
- Stroke
- Arrhythmia and conduction system disturbance
- Cardiovascular infection and sepsis (e.g., mediastinitis and endocarditis)
- Tamponade
- Sudden, unexpected death
- Other cardiovascular
- Device failure
- Death of unknown cause (adjudicated as cardiovascular)

B. Non-cardiovascular Death

Any death in which the primary cause of death is clearly related to another condition:

- Non-cardiovascular infection and sepsis (e.g., pneumonia)
- Renal failure
- Liver failure
- Cancer
- Trauma

PROPRIETARY DATA: THIS DOCUMENT CONTAINS CONFIDENTIAL AND PROPRIETARY INFORMATION OF EDWARDS LIFESCIENCES, LLC. IT MUST NOT BE REPRODUCED OR DISCLOSED TO THIRD PARTIES WITHOUT PRIOR WRITTEN PERMISSION OF EDWARDS LIFESCIENCES, LLC. [REDACTED]

[REDACTED] Edwards Lifesciences, Edwards, the stylized E logo, and EVOQUE are trademarks of Edwards Lifesciences Corporation.

 • Other non-cardiovascular

Device Deficiency (MDR 2017 definition) A device deficiency (MDR 2017) is any inadequacy in the identity, quality, durability, reliability, safety or performance of an investigational device, including malfunction, use errors or inadequacy in information supplied by the manufacturer.

Device Embolization (MVARC 2015 Definition) Device movement during or after deployment such that it loses contact with its initial position, includes detachment leading to device embolization.

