- **Secondary (non-cardiac related) heart failure:** when a non-cardiac primary condition is present such as pneumonia, urinary tract infection, or renal failure, which results in fluid overload or myocardial failure.

Note: only primary heart failure should be considered a valid criterion for heart failure hospitalization

Local Heart Team

The 'Local Heart Team', for the purpose of this study, may include one Cardiologist, one Cardiac Surgeon, one Heart Failure specialist, and one Echocardiographer.

Kansas City Cardiomyopathy Questionnaire (KCCQ)

A health-related quality-of-life measure for patients with congestive heart failure.

Katz Index of Independence in Activities of Daily Living (Katz ADL)

Completed by the site, the Katz ADL is a 6-question assessment of functional status as a measurement of the patient's ability to perform activities of daily living

Major Adverse Event (MAE)

In this study, MAEs are defined as Cardiovascular mortality, Myocardial infarction (MI), Stroke, Renal complications requiring unplanned dialysis or renal replacement therapy, Severe bleeding (includes fatal, life-threatening, extensive, or major bleeding, as defined by MVARC³), Non-elective tricuspid valve re-intervention, percutaneous or surgical, Major access site and vascular complications, Major cardiac structural complications, and Device-Related Pulmonary Embolism.

Modified Rankin Scale (mRS)

- 0: No symptoms at all
- 1: No significant disability despite symptoms; able to carry out all usual duties and activities
- 2: Slight disability; unable to carry out all previous activities, but able to look after own affairs without assistance
- 3: Moderate disability; requiring some help, but able to walk without assistance
- 4: Moderately severe disability; unable to walk without assistance and unable to attend to own bodily needs without assistance
- 5: Severe disability; bedridden, incontinent and requiring constant nursing care and attention
- 6: Dead

Mood Questionnaire

A combined anxiety and depression assessment, developed by the National Institute of Health, to be administered on the eDiary for patients participating in the sub-study.

Myocardial Infarction

(MVARC Definition)

Myocardial infarction (MI) classification and criteria for diagnosis is defined as follows:

I. Periprocedural MI (≤ 48 hours after index procedure)*†:**A. In patients with normal baseline CK-MB (or cTn):**

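### Clinical success at 30 days carries no survival condition, so a procedural success who dies of a non-cardiovascular cause without another MAE is never counted as a failure

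*SAP*

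**What the plan says.** The endpoint is built in three layers, worded alike in SAP 3.2 and Protocol 5.2, with a short form in the synopsis.

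- **Device success**, judged when the patient leaves the procedure room: "Device success is achieved if the study device is deployed as intended and the delivery system is successfully retrieved as intended".
- **Procedural success**: device success and no clinically significant paravalvular leak on the core-lab TTE at discharge.
- **Clinical success**: procedural success "without any MAEs at 30 days".

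The MAE list in Protocol 5.1, SAP 3.1 and Protocol Appendix A has nine components. Its only death component is "Cardiovascular mortality". Appendix A defines the remaining deaths as "Any death in which the primary cause of death is clearly related to another condition", with non-cardiovascular infection, renal failure, liver failure, cancer and trauma among the examples.

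For the analysis, SAP 8.2 reports clinical success per patient in the As-Treated (AT) population. It does not mention deaths outside the composite. SAP 6.1 bases event rates on patients who had the event or were followed to the end of the visit window, and leaves out patients with missing data. SAP 6.2 restricts analyses to patients with the data that the endpoint needs.

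**The concern.** A success endpoint assessed at 30 days would normally be expected to fail if the patient has died by then. Here that depends on cause of death. A patient with a good discharge echocardiogram who dies of liver failure on day 20, with no other MAE, breaks none of the stated conditions.

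Any resulting error runs in one direction, towards a higher success rate. The result also becomes sensitive to adjudication. Appendix A defines cardiovascular death through contributing conditions and non-cardiovascular death through a primary cause, so a hepatic or renal death with right heart failure in the background could arguably fit either class. That choice would decide whether the patient is a failure or a possible success. The study's stated objectives include guiding later study designs, so a weak success definition could be carried forward.

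**Working it through.** The documents report no figure for this endpoint and SAP 2.3 gives no statistical basis for the sample size, so there is no planned number to reproduce. The check is of the definitions first, then of the size of the effect.

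**Definitions applied to one patient.** Take an AT patient with the device deployed and the delivery system retrieved, no significant leak on the discharge TTE, no MAE, and a non-cardiovascular death on day 20.

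1. Device success: met. It is settled at exit from the procedure room.
2. Procedural success: met. It is settled at the discharge TTE.
3. No MAE by day 30: met. The death is not cardiovascular and no other component occurred.
4. SAP 8.2: the patient is in the AT population, so on the literal reading is a success in the denominator.
5. SAP 6.1 and 6.2: the 30-day window is ±7 days (Protocol Table 13), so it ends on day 30 + 7 = 37. The patient had no event and was not followed to day 37, so might be dropped.

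No reading makes the patient a failure because of the death.

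**Size.** Let N be the number of AT patients, s the number meeting the literal definition, and k the number of those s who died of a non-cardiovascular cause by day 30.

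- As written: s/N
- Dropped: (s − k)/(N − k)
- Counted as failures: (s − k)/N

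The literal reading exceeds the failure reading by k/N. Illustration with N = 200 (the planned maximum, all assumed to be AT) and s = 160 (assumed):

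| k | As written | Dropped | Failure | As written − failure | Dropped − failure |
|---|---|---|---|---|---|
| 1 | 80.0% | 79.9% | 79.5% | 0.5 points | 0.40 points |
| 2 | 80.0% | 79.8% | 79.0% | 1.0 points | 0.80 points |
| 4 | 80.0% | 79.6% | 78.0% | 2.0 points | 1.59 points |
| 6 | 80.0% | 79.4% | 77.0% | 3.0 points | 2.38 points |

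With 190 AT patients assumed, k/N is 1/190 = 0.53, 2/190 = 1.05 and 3/190 = 1.58 points.

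**How often.** The documents give no rate q for such deaths, so q is an assumption. The expected number in 200 patients is 200q, and the chance of at least one is 1 − (1 − q)^200.

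| Assumed q | Expected deaths | Chance of at least one |
|---|---|---|
| 0.5% | 1 | 63% |
| 1% | 2 | 87% |
| 2% | 4 | 98% |
| 3% | 6 | 99.8% |

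**Against sampling error.** At an assumed 80% success rate and N = 190, the half-width of the planned 90% normal-approximation interval is 1.645 × √(0.8 × 0.2/190) = 4.8 points.

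**The case against.** The strongest reply is that the gap is narrow, visible and small.

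- **Narrow.** Appendix A draws cardiovascular death widely. It includes heart failure, major bleeding, sudden death, cardiovascular sepsis and "Death of unknown cause (adjudicated as cardiovascular"). A renal death with new renal replacement therapy already carries an MAE. A patient who dies before the discharge TTE has not been shown to be a procedural success.
- **Visible.** SAP 9.1 tabulates primary cause of death at 30 days, SAP 9.2 summarizes and lists early adverse events, and SAP 8.4 estimates all-cause mortality from 12 months.
- **Small.** About half a point per death compares with an interval half-width of nearly five points, in a feasibility study with no hypothesis test or performance goal on this endpoint.

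All of this stands, and it limits the size of the point. It does not remove it. The separate tables report the deaths but leave the clinical success percentage unchanged. The SAP also treats survival as part of success elsewhere: its exploratory technical and device success endpoints (3.7.1, 3.7.2) both require that there was no procedural death.

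A reader might go further in three ways that the documents do not support. One is that clinical success rests on absence of MAEs alone; it requires procedural success first. Another is that every early non-cardiovascular death is counted as a success; another MAE or a failed procedural criterion prevents that, and SAP 6.1 and 6.2 leave dropping the patient as a second reading. The third is that the endpoint cannot be interpreted; the effect is bounded and the deaths can be traced in the safety tables.

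**Conclusion.** The point holds in limited form. A procedural success who dies of a non-cardiovascular cause by day 30 without another MAE cannot be a failure under the plan, and the SAP does not settle whether that patient is a success or leaves the denominator. Both readings overstate the descriptive clinical success rate relative to counting the death as a failure.

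The overstatement is up to about 0.5 points per such death, taking 190 to 200 AT patients. The number of such deaths, the 190 AT patients and the 80% success rate used for illustration are assumptions. No error rate, power figure or formal decision depends on the endpoint. The correction is still worth making: a stated rule misclassifies a patient who has died, always in the device's favour, and the remedy needs no new data.

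**What to change.** 1. In SAP 3.2, Protocol 5.2.3 and the synopsis, define clinical success as procedural success, alive at 30 days, and no MAE by 30 days.
2. In SAP 8.2, state that any AT patient who dies of any cause by day 30 stays in the denominator as a failure, whatever SAP 6.1 and 6.2 would otherwise imply. This also settles deaths that occur before the discharge TTE.
3. Leave the MAE composite unchanged.
4. If the protocol is not amended, record the change in SAP Section 10, which at present lists only the patient-centered exploratory endpoints.

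Cost: one condition in three places and one sentence in the SAP, using death dates already collected. The rate can only stay the same or fall slightly, and an early death unrelated to the device would count as a failure. Changing the protocol text needs a routine written amendment agreed with the regulator and IRB (Protocol 15.8); the SAP-only route is lighter.

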#### 3.3 Echocardiographic Endpoints and Parameters

#### 3.3.1 Echocardiographic Endpoint

• The echocardiographic endpoint is reduction in TR grade, measured by comparing the screening/baseline TTE to the discharge TTE. This endpoint will be assessed by the echo core lab using a 5-grade classification system.

#### 3.3.2 Echocardiographic Parameters

- TTE parameters will be assessed at screening/baseline, discharge, 30 days, 6 months, 1 year, and annually until 5 years post-procedure (assessed by the echo core lab)
  - 1. TR grade
  - 2. Paravalvular leak severity
  - 3. Regurgitant volume
  - 4. TV inflow gradient
  - 5. Cardiac output

### Statistical Analysis Plan for TRISCEND Study (2019-06)

- 6. Right atrium volume
- 7. Left ventricular ejection fraction
- 8. Inferior vena cava dimensions/respiratory variations
- 9. Hepatic vein flow reversal
- 10. Pulmonary artery pressure (mean)
- 11. Right ventricular function

#### 3.4 Clinical and Functional Endpoints and Parameters

- 3.4.1 Clinical and Functional Endpoints
  - The following endpoints will be assessed at 12 months and annually until 5 years post-procedure:
    - A. All-cause mortality
    - B. Heart failure hospitalizations
    - C. Non-elective tricuspid valve re-intervention, percutaneous or surgical
  - The following endpoints will be assessed at baseline, 30 days, 6 months, 12 months, and annually until 5 years post-procedure:
  - A. Volume overload assessed by serial measurements of:
    - 1. Body weight
    - 2. Edema assessment (1+ to 4+)
    - 3. Ankle circumference measurement
    - 4. Patient edema questionnaire
  - B. Functional class, functional status, and quality of life assessed by:
    - 1. New York Heart Association (NYHA) Classification
    - 2. 6-Minute Walk Test (6MWT)
    - 3. Kansas City Cardiomyopathy Questionnaire (KCCQ)
    - 4. Short Form Health Survey (SF-36v2)
- 3.4.2 Clinical and Functional Parameters
  - The following parameters will be assessed at baseline:
    - A. Canadian Study of Health and Aging (CSHA) Clinical Frailty Scale
    - B. Katz Index of Independence in Activities of Daily Living (Katz ADL)
    - C. Patient Preference Survey
  - The following general clinical and laboratory parameters will be assessed at discharge, 30 days, 6 months, 12 months, and annually until 5 years post-procedure:
    - A. Complete Blood Count (CBC)
    - B. Comprehensive Metabolic Panel (CMP)
    - C. Coagulation Panel (PT or PTT; INR for patients on vitamin K antagonist [VKA])
    - D. BNP(B-type natriuretic peptide) or NT-proBNP
    - E. GGT
    - F. Uric acid and eGFR

#### 3.4.3 Additional Safety Listings

A listing of all AEs and SAEs for the entire study population (i.e., enrolled population) will be provided.

#### 3.5 Exploratory Computed Tomography (CT) Parameters

The following parameters will be assessed at 30 days and 12 months (where data is available):

- A. Cardiac remodeling (e.g., RV dimensions and volume)
- B. EVOQUE valve frame dimensions
- C. EVOQUE valve leaflet assessment
- D. EVOQUE valve positioning

#### 3.6 Electronic Diary and Activity Monitoring Sub-study

A sub-study of up to 10 sites and up to 45 patients with data through 12 months will be conducted as follows:

Electronic Diary (eDiary): To measure quality of life improvement in greater detail, electronic patient reported outcomes will be collected via a handheld device. The following assessments will be used to measure quality of life throughout the sub-study period:

- A. KCCQ
- B. EQ-5D-5L
- C. SF-12
- D. Mood questionnaire
- E. Symptom burden

A daily assessment will be administered from baseline (for a minimum of 14 days before the index procedure) and then from post discharge through the 12-month follow-up visit.

Activity Monitoring: To measure the improvement in functional status, an activity monitor (wristwatch) will be worn by patients. The monitor is worn from baseline (for a minimum of 14 days before index procedure), paused at time of admission for index procedure, and resumed post discharge and worn through the 12-month follow-up visit.

For patients participating in the sub-study, a separate data analysis plan will be developed to analyze the actigraphy data collected from the activity monitor and electronic patient reported outcome data collected from the eDiary.

#### 3.7 Additional Patient-Centered Exploratory Endpoints

The following exploratory endpoints (based on MVARC) will be assessed for As-Treated (AT) Population.

3.7.1 Exploratory Technical Success

- Absence of procedural mortality
- Successful access, delivery, and retrieval of the delivery system

Affiliates of

Edwards

Title

Edwards

Statistical Analysis Plan for TRISCEND Study (2019-06)

- Successful deployment and correct positioning (including repositioning/recapture if needed) of the first • intended device
- Freedom from additional unplanned or emergency surgery or re-intervention related to the device or • access procedure

### 3.7.2 Exploratory Device Success

Device success will be assessed at 30 days, 6 and 12 months, and annually until 5 years post-implant procedure. All of the following must be present:

- Absence of procedural mortality or stroke •
- Proper placement and positioning of the device •
- Freedom from unplanned surgical or interventional procedures related to the device or access procedure •
- Intended safety and performance of the device including: •
  - No evidence of structural failure (e.g., major fracture, malpositioning, frozen prosthetic leaflet) or functional failure (e.g., for hemodynamic performance, the device maintains insufficiency relief without producing TV stenosis)
  - No specific device-related technical failure issues and complications (e.g., para-device complications, device-related pulmonary embolism)
  - TR reduction of at least 1 grade from baseline

Structural and functional failure will be assessed by the echo core lab. Intended safety and performance of the implanted device will be assessed at each visit. If previously identified safety or performance issues resulting in device failures at earlier visits are no longer present via TTE at a later visit (e.g., a previously identified paravalvular leak or frozen prosthetic leaflet is no longer present), a patient may be considered to have device success at the later visit.

